### 3. Introduction

#### 3.1. Study Rationale

Basaglar® (LY2963016; Eli Lilly and Company [Lilly], Indianapolis, IN, USA, and Boehringer Ingelheim, Ingelheim Rheim, Germany) and LANTUS® (Sanofi Aventis, Paris, France) are basal insulin glargine analogs that have identical amino acid sequence and similar pharmacological profiles. Basaglar received marketing approval in India on 21 August 2017 for the treatment of patients with type 1 diabetes and type 2 diabetes mellitus (T2DM) above 2 years of age. As a clause towards marketing approval, the Drug Controller General of India (DCGI), in accordance to the biosimilar guidelines for India, recommended that Basaglar be studied in a minimum of 200 additional local subjects (there were 100 subjects from India in the ELEMENT 5 study) without specific guidance towards objective of the study from an efficacy or safety perspective.

Patients with T2DM who are unable to meet glycemic targets in spite of being on oral antihyperglycemic medications (OAMs) and/or glucagon-like peptide-1 receptor agonist (GLP-1 RA) and need to initiate basal insulin, are usually preferred for treatment with Basaglar. Hence, it was decided to conduct the study in these patients. The efficacy of the drug is well established based on results from 3 randomized controlled trials in patients with type 1 diabetes and T2DM. In this study, we would seek to understand the safety of this drug in the local Indian population in accordance with the biosimilar guidelines of India.

#### 3.2. Background

Diabetes and its comorbidities present major health challenges to individuals and society at large by imposing an economic burden. Diabetes often turns fatal, thus, it has a detrimental impact on the economic burden of the society (Wild et al. 2004). The number of patients with T2DM is increasing rapidly. Of the current population burdened with T2DM, 60% are Asians (Hu 2011). Currently, India has an estimated 73 million people with diabetes, the second largest number for any individual country in the world. The projected growth between the period 2017 and 2045 in India is one of the highest in the world. By the year 2045, approximately 134 million people in India are projected to be suffering from diabetes as against 120 million in China (IDF 2017).

Insulins play an important role in the treatment of T2DM. Recent guidelines highlight the importance of initiation of basal insulin in patients with T2DM who fail to attain glycemic targets with non-insulin therapeutic options (Davies et al. 2018). Insulin initiation in India is often delayed, by almost a decade after diagnosis of diabetes. During this period, subjects are recommended various combinations of available OAMs and/or GLP-1 RA. Often, subjects are not able to achieve the glycemic targets in spite of these OAMs.

ELEMENT 5, a Phase 3, prospective, randomized, multinational, 2-arm, active-controlled, open-label, parallel-design study conducted in subjects with T2DM, showed that efficacy and safety profiles of Basaglar and LANTUS were similar (Pollock et al. 2019).

### 3.3. Benefit/Risk Assessment

There are different ways of insulin initiation in India – twice-daily neutral protamine Hagedorn insulin or once-daily LANTUS or premixed insulin. It is increasingly becoming easier to initiate subjects on long acting insulins due to its once-in-a-day dose. Evidence from several large randomized controlled trials showed that self-titration of insulin can help to reduce levels of glycated hemoglobin (HbA1c) and fasting blood glucose (FBG) without increasing the risk of hypoglycemia. This study involving glucometer-based blood glucose measurement can further substantiate the fact that subjects can self- titrate basal insulin in India without increased risk of hypoglycemia.

More detailed information about the known and expected benefits and risks of Basaglar may be found in the Patient Information Leaflet, Package Insert, or Summary of Product Characteristics.

## 4. Objectives and Endpoints

Table ABEX.2 shows the objectives and endpoints of the study.

**Table ABEX.2. Objectives and Endpoints**

Objectives	Endpoints
Primary 
 
To assess risk of hypoglycemia in adult subjects with T2DM in India who will be administered Basaglar
 
	
 
Incidence of total (symptomatic or asymptomatic with FBG level of <math>\leq 54</math> mg/dL [<math>\leq 3.0</math> mmol/L]) hypoglycemic events at Week 24
 

Secondary 
 
To assess adverse events and other safety parameters in adult subjects with T2DM in India
 
To assess efficacy of Basaglar in adult subjects with T2DM in India
 
To assess outcomes reported by adult subjects with T2DM in India
 
	
 
SAEs and TEAEs
 
Rates per 30 days and per subject year of total (symptomatic or asymptomatic) hypoglycemic events
 
Incidence and rates per 30 days and per subject-year of nocturnal, severe, documented symptomatic and asymptomatic hypoglycemic events
 
Basal insulin dose (U/day and U/kg/day)
 
Change in weight and BMI at Week 24 from baseline
 
Change in HbA1c at Week 12 and Week 24 from baseline
 
Percentage of subjects reaching HbA1c targets <math>\leq 6.5\%</math> or <math>< 7\%</math>
 
Change in FBG levels at Weeks 4, 8, and 12 from baseline
 
Self-monitored 7-point SMBG levels at baseline, Weeks 4, 8, 12, and 24
 
Change in 7-point SMBG levels at Weeks 4, 8, 12, and 24 from baseline
 
Intrabody variability, as measured by SD of 7-point SMBG levels
 
Change in Insulin Treatment Satisfaction Questionnaire scores at Week 24 from Week 4
 

Abbreviations: BMI = body mass index; FBG = fasting blood glucose; HbA1c = glycated hemoglobin; SAE = serious adverse event; SD = standard deviation; SMBG = self-monitored blood glucose; T2DM = type 2 diabetes mellitus; TEAE = treatment-emergent adverse event.

## 5. Study Design

### 5.1. Overall Design

Study I4L-IN-ABEX (ABEX) is a multicenter, open-label, single-arm, Phase 4 study to assess the safety of Basaglar in subjects with T2DM in India.

The study design includes the following periods:

[figure not shown]
- Screening (Week -2 to Week 0)
- Treatment
  - Titration period (Week 0 to Week 12)
  - Maintenance period (Week 12 to 24)
- Safety Follow-up (Week 28)

Week 0 to Week 12 will be the titration phase followed by the maintenance phase till Week 24. Approximately 295 subjects will be screened as per the inclusion and exclusion criteria mentioned in Sections [6.1](#) and [6.2](#), respectively, so that 250 subjects can be enrolled in the study, with a target to have a minimum of 200 subjects completing the present study. Subjects will be screened at Visit 1 and eligible subjects will be administered with Basaglar once daily (QD) from Visit 2 for a period of 24 weeks.

The starting dose will be 10 units QD. All subjects will be trained at Screening (Visit 1) on insulin injection administration technique, use of glucometer, and 7-point SMBG measurement. These trainings will be reinforced at every face-to-face visit of the treatment period. Subjects will self-administer Basaglar at bedtime. The doses may be titrated by 2-4 units once or twice in a week until FBG levels are lowered to <100 mg/dL (5.6 mmol/L).

Study governance considerations are described in detail in [Appendix 3](#).

Figure [ABEX.1](#) illustrates the study design.

\*Telephone visit

Abbreviations: GLP-1 RA = glucagon-like peptide-1 receptor agonist; OAM = oral antihyperglycemic medications; QD = once daily.

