Procedure	Screening	Treatment Period							Follow-up	Notes
Visit	1	2	3	4	5	6 a	7 a	8	9/ET	
Week of Study	-2	0	4	8	12	16	20	24	28	
Allowable Deviation +/- (days)		3	7	7	7	7	7	7		
Self-titration training c		X	X	X	X	X	X	X		This training is given at baseline and reinforced at every visit of the treatment period
Dispense study diary	X	X								Pretreatment study diary will be dispensed at Visit 1 and comprehensive study diary will be dispensed at Visit 2
Dispense study drug		X	X	X	X					
Review study diary		X	X	X	X			X		Pretreatment study diary will be collected at Visit 2 and comprehensive study diary will be collected at Visit 8
Collect unused study drug			X	X	X			X		
Dispense glucometer	X									
Compliance to study drug administration		X	X	X	X	X	X	X		
Adjust insulin dose (if required)			X	X	X			X		Site personnel will review the Basaglar dose and FBG levels recorded in the subject diary. They may recommend change in dose of Basaglar if required.

Abbreviations: AE = adverse event; CV = cardiovascular; DBP = diastolic blood pressure; ECG = electrocardiogram; ET = early termination; FBG = fasting blood glucose; HbA1c = glycated hemoglobin; HIV = human immunodeficiency virus; ITSQ = Insulin Treatment Satisfaction Questionnaire; PR = pulse rate; SAE = serious adverse event; SBP = systolic blood pressure; SMBG = self-monitored blood glucose; WCBP = women of child-bearing potential.

- a Telephone visit.
- b All vital signs should be recorded in the subject in a resting state. If there is a suspicion of postural hypotension or autonomic instability, the investigators at their discretion might decide to record the blood pressure in a supine state and then after standing for 2 minutes to detect any postural hypotension. Blood pressure measurements should be done in the left arm with sphygmomanometer held at the level of the heart. Blood pressure recording in both arms is at the investigators' discretion in selective cases of pulse volume inequality or pulse being absent in either of the arms.
- c Subjects will be instructed to daily measure the FBG levels mandatorily using glucometer before the morning meal till Week 12 and record in the subject diary. Also, subjects will be instructed to measure and record the blood glucose levels using glucometer if they have symptoms of hypoglycemia (including nocturnal hypoglycemia) at any time of the day or night.

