#### Treatment period (Week 0 to Week 24)

Study participants found eligible during the screening period will begin their treatment at Visit 2. All measures to be performed at Visit 2 will be done prior to administration of Basaglar. All necessary trainings will be imparted at Visits 1 and 2 and will be reinforced at subsequent visits as outlined in Section 2.

Subjects will be instructed to carry the glucometers to the sites at Visits 2, 3, 4, 5, and 8. Subjects will be instructed to measure and record the FBG levels daily before the morning meal till Week 12. Also, subjects will be instructed to measure and record the blood glucose levels if they have symptoms of hypoglycemia at any time of the day or night. Subjects will be instructed to perform 7-point self-monitored blood glucose (SMBG) level monitoring (glucose measurements before breakfast, lunch, and dinner; 2 hours after breakfast, lunch, and dinner; and at 3 am [ $\pm$  1 hour]) 2 to 3 days in the week prior to Visits 2, 3, 4, 5, and 8 and record the values in the subject diary (Section 2).

Subjects will self-administer Basaglar QD at bedtime. They will self-titrate once or twice in a week until FBG levels are lowered to  $<100$  mg/dL (5.6 mmol/L).

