## 5.5. Justification for Dose

The American Diabetes Association (2018) recommends initiation of basal insulin at 10 units or 0.1 to 0.2 unit/kg/day depending on the degree of hyperglycemia. Subjects can self-titrate once or twice in a week by 2 to 4 units or 10% to 15% to reach the target FBG level of  $<100$  mg/dL (5.6 mmol/L). In case of hypoglycemia, the dose can be reduced by 4 units or 10% to 20%. The American Association of Clinical Endocrinologists consensus statement of 2018 recommends initiation of basal insulin based on HbA1c level of 8% (total daily insulin dose: 0.2 to 0.3 unit/kg). Thus, in this study the starting dose will be 10 units QD and the dose may be titrated every 2 to 3 days to reach the glycemic goal.

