## 7. Treatments

### 7.1. Treatments Administered

Subjects will receive Basaglar QD at bedtime. The starting dose will be 10 units. Subjects can self-titrate as outlined in [Table ABEX.4](#) once or twice weekly until FBG is lowered to <100 mg/dL (5.6 mmol/L). In case of hypoglycemia, the dose can be reduced by 4 units. Subjects will continue their pre-study anti-diabetic medications at the prescribed dosage throughout the study except for risks described in Section [7.7](#). It is recommended that doses of anti-diabetic medications being taken by the subjects is stable for 90 days prior to enrolling them in this study. However, the investigator can recommend that these doses be optimized to maximum tolerated dose during 2 weeks of the screening period. If the target FBG levels are not achieved at Visit 2, the subjects are included in the study and Basaglar is initiated.

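### Titration ends at Week 12 as a phase but not in any instruction, so for subjects above target the dosing rule over half the primary hypoglycemia window can be read two ways

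*Protocol*

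**What the plan says.** Protocol Section 5.1 divides treatment at Week 12: "Week 0 to Week 12 will be the titration phase followed by the maintenance phase till Week 24". Its list of periods includes "Maintenance period (Week 12 to 24"). SAP Sections 4.1 and 7.1 use the same boundary.

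The protocol's titration instructions end differently:

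- Section 5.1: "The doses may be titrated by 2-4 units once or twice in a week until FBG levels are lowered to" under 100 mg/dL.
- Section 5.1.1, in the text headed as covering Week 0 to Week 24: "They will self-titrate once or twice in a week until FBG levels are lowered to" that same target.
- Section 5.5: "the dose may be titrated every 2 to 3 days to reach the glycemic goal".
- Section 7.1: self-titration by Table ABEX.4, "once or twice weekly until FBG is lowered to" the same target.
- Section 7.4: the same target, again with no week given.

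In the Schedule of Activities (Table ABEX.1), self-titration training is marked at Visits 2 to 8, with the note "This training is given at baseline and reinforced at every visit of the treatment period". Site dose adjustment is marked at Visits 3, 4, 5 and 8. Footnote c has subjects "daily measure the FBG levels mandatorily using glucometer before the morning meal till Week 12".

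**The concern.** Insulin dose bears directly on hypoglycemia, which is the primary endpoint. A subject whose fasting glucose is still above target at Week 12 has left the titration phase but has not met the stopping condition in any titration instruction. A site relying on the phase definition would hold the dose. A site relying on Section 5.1.1 or 7.1, and on the training row, would let the subject keep adjusting.

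Three things are at stake.

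- **Safety.** Under the second reading, subjects adjust their own insulin without the daily fasting readings that guided them up to Week 12.
- **Consistent exposure.** This is a single-arm trial, so site differences in dosing after Week 12 go straight into the one estimate of incidence, and into Week 24 dose and HbA1c.
- **Compliance.** Section 7.6 assesses compliance partly against the titration algorithm and asks for deviations to be recorded. A site cannot tell whether a dose increase at Week 16, or the lack of one, is a deviation.

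**Working it through.** **1. The plan's own figures.** Table ABEX.3 gives 95% half-widths for the primary incidence at n = 250. With 1.96 × √(p(1−p)/n):

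- p = 0.11: 1.96 × √(0.11 × 0.89/250) = 3.88%; the table has 3.9%.
- p = 0.30: 1.96 × √(0.30 × 0.70/250) = 5.68%; the table has 5.7%.

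These reproduce. The point does not dispute them.

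**2. What ends titration, place by place.**

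| Place | What ends titration | Week named? |
|---|---|---|
| Protocol 5.1, phase definition; SAP 4.1 and 7.1 | End of titration phase | Week 12 |
| Protocol 5.1, dosing sentence | Fasting glucose target | No |
| Protocol 5.1.1 | Fasting glucose target | No; heading runs to Week 24 |
| Protocol 5.5 | Glycemic goal | No |
| Protocol 7.1 | Fasting glucose target | No |
| Protocol 7.4 | Fasting glucose target | No |
| SAP 4.1, dosing sentence | Fasting glucose target | No |

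The two kinds of rule agree for a subject who reaches target by Week 12. They diverge for a subject who does not.

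**3. What the schedule supports after Week 12.**

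- Training: self-titration is reinforced at Visits 6 and 7 (Weeks 16 and 20, by telephone), which fits continued titration.
- Daily fasting glucose: mandatory only to Week 12, which fits a dose held from Week 12.
- Other scheduled fasting values: the pre-breakfast point of the 7-point profile, on 2 to 3 days in the week before Visit 8. Readings prompted by symptoms are unscheduled.
- Rescue: the Section 7.4 limit from Week 12 to end of trial presumes 4 values a week and refers to 2 consecutive weeks. The schedule gives at most 3 values, in one week, so it cannot supply what the limit needs.

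The phase, titration, training, monitoring and rescue provisions therefore cannot all be followed together after Week 12.

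**4. Share of the primary window.** SAP Section 19 counts events from Visit 2 to Visit 8. SAP Section 7.1 puts Weeks 0, 12 and 24 at Days 0, 84 and 168. The share after Week 12 is (168 − 84)/168 = 50%. Protocol Section 10.3.2.1 counts events over the study period; if that ran to Week 28 (Day 196), the maintenance phase would be 84/196 = 43%.

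**5. A scale check, on assumptions that are not in the documents.** Suppose a constant hazard giving 24-week incidence p, and multiply the hazard after Week 12 by r between 0.5 and 2. Incidence becomes 1 − exp(−(H/2)(1 + r)), with H = −ln(1 − p).

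- p = 0.11 (H = 0.1165): 8.4% at r = 0.5 and 16.0% at r = 2.
- p = 0.30 (H = 0.3567): 23.5% at r = 0.5 and 41.4% at r = 2.

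The shifts (−2.6 to +5.0 points, and −6.5 to +11.4 points) are of the same order as the half-widths in step 1. The calculation applies r to every subject, although only those above target at Week 12 are affected. It shows that the ambiguity could matter at the scale of the planned precision and does not estimate an effect.

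**The case against.** The best defence is that Section 5.1 gives the phases and the titration sentence together, so the glucose target can be read as operating inside a phase that closes at Week 12. Daily fasting glucose to Week 12 and the fasting glucose endpoint at Weeks 4, 8 and 12 fit that reading. Sections 5.1, 5.5 and 7.4 say the dose may be titrated and 7.1 says subjects can titrate; only 5.1.1 is worded as something they will do. The training note matches the one on the hypo/hyperglycemia training row, so it may be generic, and reinforcing the scheme also covers its zero and downward steps.

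This makes a held dose a reasonable reading, but not the only one. Section 5.1.1 sits under a heading that runs to Week 24, and no passage says that titration closes with the phase. The defence also leaves the rescue limit without readings.

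Four stronger readings are tempting, and the documents do not support them.

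- **That the data could not separate held from titrated dosing.** Every dose is diarised and entered in the eCRF (Protocol 7.2.1), daily dosing is listed by subject (SAP 12.2), and each hypoglycemic event has a start date (SAP 19.1.1).
- **That doses could climb by 24 to 96 U after Week 12** (2 U × 1 × 12 weeks to 4 U × 2 × 12 weeks). This needs fasting glucose to stay in one band despite the added insulin. Table ABEX.4 is self-limiting: the step is zero at 80-100 mg/dL and negative below 80.
- **That Week 24 training adds to the problem.** That visit closes the SAP's primary window, so training there can hardly affect the endpoint. Weeks 16 and 20 carry the point.
- **That titration has no stopping rule.** It has one, the glucose target. Only a limit in time is unstated.

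**Conclusion.** The point holds as a contradiction between the plan's dosing, training, monitoring and rescue provisions after Week 12, and it should be fixed. It covers 84 of 168 days of the SAP's primary window, but that is a share of calendar time, not of subjects. It applies to subjects above target at Week 12, and the documents give no figure for how many that will be. It does not invalidate the trial.

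One condition applies. The study-design figures (Protocol Figure ABEX.1 and SAP Figure 7.1) are not shown in the text reviewed and may label dosing by phase. Even so, the written passages would still need to agree with them. The effect on the PPS is possible but not established: SAP Section 6.3 removes subjects with a major deviation, and the documents do not say how a dose change after Week 12 would be graded.

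**What to change.** Reconcile Protocol Sections 5.1, 5.1.1, 5.5, 7.1 and 7.4, the self-titration training, dose-adjustment and FBG rows of Table ABEX.1, and SAP Section 4.1, so that all state the same rule on self-titration after Week 12. Set the fasting glucose schedule after Week 12 so that it supports both that rule and the Section 7.4 rescue limit. Which rule applies is for the sponsor's clinicians.

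Optionally, add one SAP table giving hypoglycemia and dose change for Weeks 0-12 and Weeks 12-24. It needs no new data. It should carry a note that less fasting glucose testing after Week 12 lowers the detection of asymptomatic events, so a lower count in the second phase would not by itself show lower risk.

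The cost is amended wording in both documents and, if chosen, one table. If the schedule is extended to match the rescue limit, subjects take more home readings with the glucometers and strips that Section 7.1.2 already provides.

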**Figure ABEX.1. Illustration of study design for clinical protocol I4L-IN-ABEX.**

### 5.1.1. Study Visits

#### Screening period (Week -2 to Week 0)

Multiple procedures will be done during the screening period to assess eligibility of subjects for inclusion in the study (Sections 6.1 and 6.2) as specified in the Schedule of Activities (Section 2). Subjects will be provided glucometers and study diaries at Screening (Visit 1).

#### Treatment period (Week 0 to Week 24)

Study participants found eligible during the screening period will begin their treatment at Visit 2. All measures to be performed at Visit 2 will be done prior to administration of Basaglar. All necessary trainings will be imparted at Visits 1 and 2 and will be reinforced at subsequent visits as outlined in Section 2.

Subjects will be instructed to carry the glucometers to the sites at Visits 2, 3, 4, 5, and 8. Subjects will be instructed to measure and record the FBG levels daily before the morning meal till Week 12. Also, subjects will be instructed to measure and record the blood glucose levels if they have symptoms of hypoglycemia at any time of the day or night. Subjects will be instructed to perform 7-point self-monitored blood glucose (SMBG) level monitoring (glucose measurements before breakfast, lunch, and dinner; 2 hours after breakfast, lunch, and dinner; and at 3 am [ $\pm$  1 hour]) 2 to 3 days in the week prior to Visits 2, 3, 4, 5, and 8 and record the values in the subject diary (Section 2).

Subjects will self-administer Basaglar QD at bedtime. They will self-titrate once or twice in a week until FBG levels are lowered to  $<100$  mg/dL (5.6 mmol/L).

### Follow-up Visit (Week 28)

All subjects will have a follow-up visit 4 weeks after the last dose of Basaglar. Assessments at this visit will be done as detailed in Section 2. Subjects who withdraw from the study will also have assessments done similar to those at the follow-up visit.

### **5.2. Number of Participants**

Assuming a 15% screen failure rate, approximately 295 subjects will be screened, so that 250 subjects can be enrolled. Assuming a drop-out rate of 20%, the target is to have a minimum of 200 subjects completing the present study.

In the India subpopulation of ELEMENT 5 study, 5 of the 46 insulin-naïve subjects experienced at least 1 hypoglycemic event (total hypoglycemia incidence with glucose levels  $\leq 54$  mg/dL [3.0 mmol/L]) during the overall study period. When considering the total ELEMENT 5 population, 146 out of 489 subjects (30%) experienced at least 1 hypoglycemic event during the overall study period. Based on these estimates, the precision with 250 and 200 subjects would be as outlined in [Table ABEX.3](#) (95% confidence interval for proportion shown based on normality assumption).

